Title of Study: Toileting at Night in Older Adults: Light to Maximize Balance, Minimize Insomnia

NCT number: NCT01350505

Date of document: 9/26/18

Initial analysis plan

To test our Primary Hypothesis that a long wavelength light stimulus delivered at night will improve gait and not change alertness, we will examine stride-to-stride variability in speed and change in EEG delta power as our two primary outcome measures. Statistical significance will be determined with independent repeated measure analyses of variance (ANOVA) with *post hoc t*-tests. Our *a priori* hypothesis is that gait will be progressively improved such that dim light < orange light = room light and that alertness will be improved such that dim light = orange light < room light.

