Title of Study: Toileting at Night in Older Adults: Light to Maximize Balance, Minimize Insomnia

NCT number: NCT01350505

Date of document: 9/26/18

Initial protocol

Study Procedures

Subjects will be initially phone screened before being asked to come to the lab for a screening visit. By including the phone screen, we have found that our failure rate during the screening visit is relatively low (around 20%). Our previous experience indicates that relatively few of the randomized subjects will be disempaneled. Subjects will be randomized after passing their lab screening visit; subjects who are disempaneled will be replaced. Subjects will be block randomized in three groups of nine (three in each condition), with drop-outs replaced. In-person screening will consist of discussion and signing of the consent form and completion of the following forms or tests: demographics, medication/health log, Owl and Lark Questionnaire ('morningness'/'eveningness'), Ishihara Color Plate (color blindness), Mini Mental State Exam (dementia), Pittsburgh Sleep Quality Index (sleep disorders), Geriatric Depression Scale, AUDIT (alcoholism), Balance Self-efficacy Scale (self-assessed balance), Nocturia, Nocturnal Enuresis and Sleep-interruption Questionnaire, Octopus 900 (peripheral vision), and ETDRS (visual acuity).

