After 2 hours in darkness subjects, will be awakened by the technician into one of the three experimental lighting conditions (dim white light, room light, dim orange light) and be kept awake for 13 minutes. Subjects will be tested with the same sequence as at baseline. Following the 13-minute experimental light exposure, subjects will be allowed to sleep in darkness until their typical wake time. Upon awakening, subjects will be given a subjective test of alertness (Stanford Sleepiness Scale), an objective test of alertness (Psychomotor Vigilance Test), and a questionnaire regarding the previous night of sleep (Groningen Sleep Quality Questionnaire). They will then be provided a standard hospital breakfast and discharged.

Exposure to the experimental light will always start two hours after habitual bedtime and last 13-minutes. The first two conditions, very dim white light (0.5 lux, low mesopic range) and dim white room light (5 lux). The illuminance will be confirmed with a photometer (IL1700, International Light, Peabody MA). The orange light condition will be produced by filtering the fluorescent lamps with an acrylic filter (Roscolux #19 "Fire", Roscolux, Glendale CA) so as to produce 1×10^{13} photons \cdot cm $^{-2}$ \cdot s $^{-1}$ or an equivalent LED light.

As a follow-up to this original protocol, subjects who completed all three of the visits previously described, and who indicated a willingness to be recontacted, will be asked to sign a new consent form and participate in a single overnight visit (with preceding at-home sleep monitoring) identical to the described, except that they will be awoken into normal room light (150 lux).

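### The unchanged-alertness half of the primary hypothesis has no test that could support it: the plan names only significance tests

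*SAP*

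**What the plan says.** The SAP (Initial analysis plan) states a "Primary Hypothesis that a long wavelength light stimulus delivered at night will improve gait and not change alertness". It continues: "we will examine stride-to-stride variability in speed and change in EEG delta power as our two primary outcome measures". The gait variable serves the improvement claim, and delta power serves the claim about alertness.

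The method is one sentence: "Statistical significance will be determined with independent repeated measure analyses of variance (ANOVA"), followed by post hoc t-tests. The expected pattern is "dim light < orange light = room light and that alertness will be improved such that dim light = orange light < room light", the first ordering being for gait. Of the six pairwise relations in the two orderings, four are differences and two are equalities: orange and room light for gait, orange and dim light for alertness.

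The Protocol (Study Procedures) has no analysis text. It bears on sample size and design only through "Subjects will be block randomized in three groups of nine (three in each condition), with drop-outs replaced" and, in the closing follow-up paragraph, "subjects who completed all three of the visits previously described".

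**The concern.** The main claim joins a gait benefit to unchanged alertness. The gait half is a difference and can be tested as planned. The alertness half is a claim of no difference, and the named tests take no difference as their null hypothesis. Failing to reject a null hypothesis does not support it.

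The only orange-versus-dim result on delta power that would agree with the hypothesis is therefore a non-significant one. That result becomes more likely with fewer subjects, noisier EEG data or a stricter adjustment of the post hoc tests, so a weaker study would find it easier to appear to confirm the claim. A real alerting effect of orange light could pass as no change. The study is about lighting that helps balance at night without costing sleep, so this part of the conclusion matters as much as the gait result.

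**Working it through.** **What each planned test can show (alertness ordering)**

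| Relation | Type of claim | Can a significant t-test support it? |
|---|---|---|
| dim < room | difference | yes |
| orange < room | difference | yes |
| dim = orange | no difference | no; it can only contradict it |

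Only the third row corresponds to the alertness part of the primary hypothesis. Neither document contains a margin, an interval criterion, an equivalence or non-inferiority test, or a Bayesian criterion. This step needs no numbers.

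**Size, as an illustration.** The documents give no alpha, SD, power calculation or margin, so there is no planned figure to reproduce. Inputs:

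- n = 27: assumed from three groups of nine (Protocol, Study Procedures).
- Paired data: inferred from the repeated measures ANOVA (SAP) and the three visits per subject in the follow-up paragraph (Protocol).
- Two-sided alpha 0.05, or 0.05/3 = 0.0167 if the three pairwise tests are Bonferroni-adjusted: assumed.
- Effects d and margins m in units of the SD of the paired difference: assumed ranges.

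*Chance of a non-significant result when a true difference d exists.* With T following a noncentral t distribution on 26 df and noncentrality d√27 (√27 = 5.196), this is P(|T| < c), where c = 2.056 at 0.05 and 2.559 at 0.0167.

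| d | d√27 | at 0.05 | at 0.0167 |
|---|---|---|---|
| 0.3 | 1.559 | 0.676 | 0.821 |
| 0.4 | 2.078 | 0.483 | 0.666 |
| 0.5 | 2.598 | 0.294 | 0.476 |

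The chance is 50% at d = 0.39 (alpha 0.05) and at d = 0.49 (alpha 0.0167).

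*Other readings of the sample size.* At 0.05 and d = 0.5, nine pairs would give a non-significant result 74% of the time. With nine per independent group and a difference of 0.5 between-subject SD, the figure is 83%.

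*What a valid test would deliver, true difference 0.* TOST succeeds when the 90% CI lies inside ±m; power was found by integrating over the sample variance. One-sided 5% non-inferiority power is P(T > 1.706) with noncentrality m√27.

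| Margin m | TOST power, 27 pairs | NI power, 27 pairs | Pairs for 80%, TOST | Pairs for 80%, NI |
|---|---|---|---|---|
| 0.4 | 0.300 | 0.648 | 55 | 41 |
| 0.5 | 0.624 | 0.812 | 36 | 27 |
| 0.6 | 0.836 | 0.918 | 26 | 19 |

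The smallest margin with 80% power at 27 pairs is 0.58 SD for TOST and 0.49 SD for non-inferiority. When the sample SD equals the true SD, the 90% CI half-width is 1.706/5.196 = 0.33 SD, so TOST margins at or below that are practically out of reach.

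**The case against.** The plan predicts a pattern, not an isolated null. If room light separates from both other conditions, delta power has been shown to respond to light, and a null between orange and dim is then more informative than it would be alone. That is fair, and it is a reason to keep those tests. It does not close the gap: orange could be less alerting than room light and still more alerting than dim.

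The SAP also never says that a non-significant result will be read as no change, and its equality signs may be shorthand for an expected pattern. The first part is true. But the plan says it will test a primary hypothesis containing this claim, and it offers no other route to it. The shorthand reading is more plausible for orange versus room on gait, which the primary hypothesis does not mention.

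The hypothesis sentence does not name the comparator for unchanged alertness; the ordering "alertness will be improved such that dim light = orange light < room light" supplies it, though the SAP should say so outright. Finally, the percentages rest on assumed n, pairing, alpha and SD units, and the Bonferroni column models an adjustment that the plan does not mention. That stands, so the figures show scale only. A full equivalence test may also be more than the sample can bear, which is why the fix includes a route without a margin.

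**Conclusion.** The concern holds. The method does not fit the question asked: followed as written, the alertness half of the primary hypothesis can be rejected but not supported. This follows from the wording of the SAP and depends on no assumed number. The gait improvement and the predicted contrasts with room light on alertness remain testable.

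Under the 27-pair reading, moderate true differences (0.3 to 0.5 SD of the paired difference) would go undetected between 29% and 68% of the time at 0.05, and between 48% and 82% with a three-way Bonferroni adjustment. Smaller readings of the sample make this worse. It should be fixed before analysis.

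**What to change.** 1. **Orange versus dim on delta power.** State this comparison as the alertness part of the primary hypothesis and base the conclusion on its confidence interval. Fix and justify a margin before analysis, and claim no change only if the 90% CI lies inside it (TOST). If the worry is only that orange is more alerting than dim, restate the claim as not more alerting, say which direction of delta power counts as more alert, and use a one-sided 5% non-inferiority test.
2. **Difference claims.** Keep the planned t-tests for dim versus orange and dim versus room (gait), and for orange versus room and dim versus room (alertness). Call the primary hypothesis supported only if orange beats dim on gait and the orange-versus-dim alertness criterion is met. Both must succeed, so no alpha split is needed.
3. **Orange versus room on gait.** Treat it as a secondary prediction, with its own margin or reported with its CI.
4. **Without a margin.** If none can be justified, or the sample is too small for it, report the CI and write that no difference was shown, not that the conditions are equal.

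The cost is SAP wording and one justified margin, with a second only if equality on gait is to be claimed. The alertness claim becomes harder to win, as the power table shows. Non-inferiority is cheaper but gives up the two-sided wording. Step 4 needs no margin and no extra subjects.

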
After the one-week, at-home protocol, subjects will come to the laboratory three hours before their scheduled bed time. Following confirmation of their at-home sleep schedule, subjects will produce a

urine and saliva sample. Urine will be tested for the presence of common illegal drugs (cocaine, tetrahydrocannabinol, methamphetamine; DrugCheck3, Express Diagnostics; result in 5 minutes) and saliva will be tested for the presence of alcohol (Chematics, Alco-Screen 02; result in 4 minutes). The presence of illegal drugs or alcohol (>0.02% blood alcohol content) will result in dispanelment. Other than indicating in the medical record that the subject was dispaneled for cause, no other record of the drug and alcohol tests will be kept. Cleared subjects will be brought to the Stanford University/VA Palo Alto Health Care System Sleep and Circadian Translational Research Laboratory (SCTRL). During their entire stay at the SCTRL, subjects will remain in a time isolation suite (no windows, no clocks or other time cues, *en suite* bathroom, regulated temperature of 70 °F, all lighting controlled from outside the suite). Upon entry into the SCTRL until the subject leaves the next morning, illuminance is kept at normal room lighting (~150 lux in any angle of gaze) except during hours of scheduled darkness (<0.03 lux) and the 13-minute experimental light stimulus. In the SCTRL, the floors are white and the walls are painted with a white, titanium dioxide-based paint that increases luminosity and ensures a relatively even illuminance across the room.

After entry into the SCTRL, subjects will have a baseline testing sequence: Stanford Sleepiness Scale (subjective sleepiness), visual acuity testing, peripheral vision testing, mobile balance testing (walking on a specialized, pressure-sensing walkway), Karolinska Drowsiness Task (EEG monitoring of drowsiness), mobile balance testing, auditory version of the Psychomotor Vigilance Test (objective alertness), a five minute break while seated, and the sequence repeated. During this testing, brain wave activity (electroencephalogram, electromyogram) and eye movements (wireless eye tracking) will be monitored. This will serve as a baseline test to account for interindividual variability. Subjects will go to sleep at their habitual bed time (calculation described above).

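### Both primary outcomes have a pre-sleep baseline at each visit, but the SAP does not say how it enters the analysis; adjusting the night value for it is a low-cost gain in precision

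*SAP*

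**What the plan says.** The SAP is one paragraph, under Initial analysis plan. It states: "we will examine stride-to-stride variability in speed and change in EEG delta power as our two primary outcome measures". The test is given as "Statistical significance will be determined with independent repeated measure analyses of variance (ANOVA"), followed by post hoc t-tests. No covariate is named, and neither is the repeated factor. Gait variability appears without mention of a baseline. Delta power appears as a change, without saying from what, over which EEG segment or on which scale.

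The protocol, under Study Procedures, describes a test sequence after laboratory entry and before sleep. It covers both outcomes: "mobile balance testing (walking on a specialized, pressure-sensing walkway), Karolinska Drowsiness Task (EEG monitoring of drowsiness), mobile balance testing". The whole is run twice: "a five minute break while seated, and the sequence repeated". Its purpose is stated: "This will serve as a baseline test to account for interindividual variability". At the night awakening, under the experimental light, "Subjects will be tested with the same sequence as at baseline".

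That this recurs at each of three visits is inferred from the follow-up paragraph, which refers to "subjects who completed all three of the visits previously described". The randomization sentence can be read differently: "Subjects will be block randomized in three groups of nine (three in each condition), with drop-outs replaced".

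**The concern.** The protocol gives the evening measurement a purpose, and the SAP does not say how that purpose is met. Two consequences follow, both about precision.

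For gait, if the analysis uses only the night value, information already collected goes unused.

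For delta power, the natural reading is night minus evening. Subtraction fixes the weight of the evening value at 1. In a within-subject comparison, stable differences between subjects cancel anyway, so the evening value can help only with visit-to-visit variation. If it predicts that variation weakly, subtracting it adds noise.

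Precision matters here because the hypothesis predicts equalities as well as differences: orange equal to room light for gait, and dim equal to orange for alertness. A claim of equality is only as good as the width of its interval.

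**Working it through.** The documents give no SD, correlation, effect size or power, so there is no figure of theirs to reproduce.

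**Inputs**
- Subjects: 3 x 9 = 27, inferred from the randomization sentence, all assumed to complete.
- Visits: three per subject, from the follow-up paragraph (crossover reading).
- rho: within-subject, same-visit correlation of evening and night values. Assumed, 0 to 0.7.
- k: evening SD divided by night SD, both within subject. Assumed, 0.5 to 1.5.
- w: correlation between evening walks. Assumed, 0.5 to 0.9.

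**Cost of estimating the slope**
- Pooled crossover: 27 x 3 = 81 observations. Error df before adjustment = 81 - 27 (subject) - 2 (condition) - 2 (visit) = 50. Expected factor 1 + 1/(50 - 2) = 49/48 = 1.021.
- Separate paired tests: df 26, factor 1 + 1/24 = 1.042.
- Parallel, 9 per condition: df 24, factor 1 + 1/22 = 1.045.

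**Contrast variance, in units of the night residual variance**
- Night value alone: 1
- Night minus evening: 1 + k² - 2·rho·k. This exceeds 1 when rho < k/2.
- Night value with baseline covariate: (1 - rho²) x factor

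**Gait: adjusted against night value alone**

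| rho | pooled | separate paired tests |
|---|---|---|
| 0 | 1.021 (+2%) | 1.042 (+4%) |
| 0.2 | 0.980 (-2%) | 1.000 (0%) |
| 0.5 | 0.766 (-23%) | 0.781 (-22%) |
| 0.7 | 0.521 (-48%) | 0.531 (-47%) |

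Break-even rho = sqrt(1 - 1/factor) = 0.14 pooled and 0.20 paired.

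**Delta power: change-score variance divided by adjusted variance (pooled)**

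| k | rho 0.2 | rho 0.5 | rho 0.7 |
|---|---|---|---|
| 0.5 | 1.07 | 0.98 | 1.06 |
| 0.75 | 1.29 | 1.06 | 0.98 |
| 1 | 1.63 | 1.31 | 1.15 |
| 1.5 | 2.70 | 2.29 | 2.21 |

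Example, k = 1 and rho = 0.5: (1 + 1 - 1) / (0.75 x 1.021) = 1.31. At k = 1 the square roots give intervals 28%, 14% and 7% wider. At k = 0.5 and 0.75, five of the six cells lie between 0.98 and 1.07.

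**Averaging the evening walks.** Two walks per run and two runs give up to four walks. The mean of m readings has rho_m = rho_1 x sqrt(m / (1 + (m - 1)w)). With rho_1 = 0.5 and m = 4:

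| w | rho_4 | adjusted variance, pooled |
|---|---|---|
| 0.5 | 0.63 | 0.61 (-39%) |
| 0.8 | 0.54 | 0.72 (-28%) |
| 0.9 | 0.52 | 0.74 (about -26%) |

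One walk alone gives -23%. Averaging the night readings is not modelled.

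**Night value or change as the outcome.** If night = condition effects + b x evening + error, then night - evening = the same condition effects + (b - 1) x evening + error. The condition contrasts are identical. This needs change to be a plain difference on the scale of the covariate; it fails for percent of baseline.

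**Simulation check** (27 subjects, fixed subject and visit effects, an assumed balanced order, k = 1, 4,000 trials per rho). At rho 0.2, 0.5 and 0.7, change/adjusted was 1.59, 1.31 and 1.16. At rho 0, 0.2, 0.5 and 0.7, adjusted/unadjusted was 1.03, 0.97, 0.75 and 0.52. These agree with the formulas.

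**The case against.** The strongest reply is that the SAP is silent rather than wrong. A reader might infer that the plan excludes the baseline from the gait analysis. The text does not support that: the repeated factor is unnamed, and if it includes evening versus night, gait already uses the baseline. The protocol's stated purpose also points to some use. This stands, and the point is therefore put as an unstated choice.

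Second, repeated measures already make each subject their own control, which meets the stated purpose of the baseline in a crossover. This also stands. What remains to gain concerns visit-to-visit variation only. Nobody should read the point as a claim of bias; the change score is unbiased.

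Third, every magnitude rests on assumed correlations. True, and the ranges include cases with no gain. It would be wrong to infer that a change score is always clearly worse, or that averaging walks always brings -39%. That figure needs walks in one evening to correlate no better with each other than with a walk after two hours of darkness.

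Fourth, a reader might treat the missing rule for combining readings as a serious defect in its own right. It is an omitted detail that would not carry the point alone; it belongs with the definition of the baseline.

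Finally, the design is not settled. The allocation of three per condition within blocks of nine can be read as parallel groups. The rho values above would not then apply, because rho would include stable subject differences. The case for a covariate survives under either reading.

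**Conclusion.** The point holds as one of precision and specification. A baseline for both primary outcomes precedes the light, so that visit's condition cannot affect it, and the SAP does not say how it is used. Adjustment is nearly free and may help substantially. For gait, the gain over the night value alone is nil or slightly negative below a correlation of about 0.14 (0.20 in paired tests), and useful from about 0.5. For delta power, the gain over a simple change score is clear when evening and night SDs are similar or the evening SD is larger, and small or absent in most cases when the evening SD is 0.5 to 0.75 of the night SD.

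These sizes assume a crossover, 27 completers, pooled error and the stated ranges of rho, k and w. The change should be made before analysis, but its absence does not invalidate the planned comparison. Confidence is medium, because the quantities that set the gain are not in the documents.

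**What to change.** Amend the SAP so that, for both primary outcomes:
- the outcome is the night value and that visit's evening baseline is a covariate. If the trial is a crossover, include condition, visit number and a fixed subject effect, and take the condition contrasts from this pooled model. If it is parallel, use condition plus baseline. State which design applies;
- the baseline is the mean of the evening readings (both runs, and both walks within each run for gait), with night readings combined by the same rule;
- the EEG segment and scale that give delta power are stated. The protocol monitors EEG throughout testing, and the SAP does not tie delta power to the drowsiness task. The word change can stay if defined as an additive difference on that scale.

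The cost is wording and one error degree of freedom; no new data are needed. If the baseline proves uninformative, expected variance inflation is about 2% pooled, 4% in separate paired tests and 4.5% in a parallel design. These are averages: taking realised inflation as F(1, df)/df, one trial in 20 would exceed about 8%, 16% and 18%. The model also assumes a common slope across lights and, for pooled contrasts, equal error variance across lights. Both assumptions should be stated, with contrasts from separate paired comparisons, baseline included, as a sensitivity analysis.

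### The SAP predicts an ordering of the three lights for each primary outcome, but decides significance with an any-difference ANOVA and post hoc t-tests it does not name

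*SAP*

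**What the plan says.** The SAP (Initial analysis plan) names "stride-to-stride variability in speed and change in EEG delta power as our two primary outcome measures". It states a prediction for each: "gait will be progressively improved such that dim light < orange light = room light", and "alertness will be improved such that dim light = orange light < room light".

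The decision rule is one sentence: "Statistical significance will be determined with independent repeated measure analyses of variance (ANOVA"), with post hoc t-tests to follow. The SAP does not say which pairs are tested, whether the t-tests depend on a significant F, or what alpha, sidedness or adjustment applies. It names no planned contrast.

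The Protocol (Study Procedures) has three lighting conditions. On numbers it says: "Subjects will be block randomized in three groups of nine (three in each condition), with drop-outs replaced". The follow-up paragraph refers to "subjects who completed all three of the visits previously described", which together with the repeated-measures analysis points to every subject being seen in all three lights.

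**The concern.** The test and the prediction do not match. A significant gait F would also arise if only room light helped and orange did no better than dim. That would contradict the primary hypothesis, which is about long-wavelength light. The claim would then rest on t-tests described as post hoc, with the choice of pair open until the data are seen.

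There is also a power issue. ANOVA followed by post hoc t-tests is usually run with the t-tests conditional on a significant F. Read that way, orange versus dim on gait, the comparison that carries the claim, must pass two tests. In a trial this small that lowers the chance of confirming a prediction fixed in advance.

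**Working it through.** The documents give no power figure to reproduce, so the size has to be worked out under stated assumptions.

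**Inputs**
- Conditions: 3 (Protocol, Study Procedures).
- Subjects: three groups of nine, 3 × 9 = 27, drop-outs replaced (same section).
- Layout: each subject seen in all three lights (inferred, as above).
- Assumed, because not stated: two-sided 0.05; independent errors of equal variance within subject.
- *d* is the gap between two lights in within-subject SDs, oriented so that positive means better.

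**Formulas, gait prediction exactly true (dim 0, orange *d*, room *d*)**
- The deviations from the mean are −2*d*/3, *d*/3, *d*/3. Their squares sum to 2*d*²/3, so λ = 27 × 2*d*²/3 = 18*d*².
- Omnibus test: noncentral F with 2 and 52 df and noncentrality λ.
- Pattern contrast (−2, +1, +1) from per-subject scores: noncentral t, 26 df, noncentrality √λ.
- Orange minus dim from per-subject differences: noncentral t, 26 df, noncentrality *d*√(27/2) = 3.674*d*. At *d* = 0.7 this is 2.572.
- Orange minus dim *after* a significant F: simulation, 60,000 trials per setting.

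**Orange versus dim**

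| *d* | Significant F required first | Not conditional on F | Gain (points) |
|---|---|---|---|
| 0.5 | 34% | 42% | 8 |
| 0.7 | 64% | 70% | 6 |
| 0.8 | 77% | 81% | 4 |

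**Pattern contrast against omnibus F**

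| *d* | λ | F | Contrast (26 df) | Gain (points) |
|---|---|---|---|---|
| 0.5 | 4.50 | 43.8% | 53.3% | 9.5 |
| 0.6 | 6.48 | 59.3% | 68.8% | 9.5 |
| 0.7 | 8.82 | 73.6% | 81.6% | 8.0 |
| 0.8 | 11.52 | 84.8% | 90.4% | 5.6 |
| 0.9 | 14.58 | 92.4% | 95.7% | 3.3 |

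**If the prediction is wrong**
- *Orange halfway* (0, 0.35, 0.7): λ = 27 × (0.35² + 0.35²) = 6.615, so F has 60%. The pattern contrast has noncentrality 1.05/√(6/27) = 2.227 and power 57%. Orange minus dim has noncentrality 0.35 × 3.674 = 1.286 and power about 24%, because the gap being tested is half as large.
- *Orange does nothing, room +0.7*: λ is again 8.82, so F is significant 74% of the time. The pattern contrast has noncentrality 0.7/√(6/27) = 1.485 and is significant 30% of the time. Orange minus dim is significant 5% of the time, its nominal error rate.

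The last case settles which comparison should decide. Both the F and the pattern contrast can be significant through room light alone; only orange minus dim keeps its error rate for the gait claim.

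**If the layout were parallel** (9 per condition, 24 error df): at a gap of 1.35 SD, where F has 80% power, orange versus dim is significant in 73% of simulated trials if F is required first and in 78% if not.

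**The case against.** ANOVA with post hoc t-tests is conventional and valid, and the t-tests can reach every predicted pair. With three conditions and the usual assumptions, a significant F followed by unadjusted pairwise tests also controls familywise error over all three pairs. That is true, and it is what the F gate buys. The protection is not needed within an outcome when a single comparison is named in advance.

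The SAP does not state that the t-tests depend on the F. This also stands: the gain in orange-versus-dim power applies to the usual reading. If the t-tests are run regardless, what remains is the unnamed pair and the absence of any error rule.

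A reader might infer a fixed loss of around 10 points that planned contrasts would recover for nothing. The documents do not support that. They give no effect size, SD, correlation, alpha or power; the gain shrinks as power rises; and the contrast loses to the F if orange is only about halfway. The SAP's own word, progressively, makes an intermediate orange effect plausible.

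A reader might also infer that the pattern contrast should become the decision test. It should not, since room light alone can drive it. Nor should it be a gate: requiring it before orange minus dim gives 67.5% at *d* = 0.7, against 64% behind the F and 70% with no gate.

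Finally, none of these comparisons shows equality. That objection stands in full and has to be met separately.

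**Conclusion.** The point holds as a mismatch between the stated hypotheses and the decision test, with a modest cost in power. The mismatch is in the text and needs no assumption. The size does: for 27 subjects in all three lights, independent errors, two-sided 0.05 and the predicted pattern true, freeing orange versus dim from the F gate adds about 4 to 8 points for *d* between 0.5 and 0.8. The pattern contrast gains roughly 3 to 10 points over the F for *d* between 0.5 and 0.9, but loses a few if orange lies about halfway between dim and room.

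Orange minus dim is not more powerful than the F for detecting *some* difference (70% against 74% at *d* = 0.7). Its advantage is that a significant result means what the SAP wants to claim. The planned ANOVA is not invalid; the change is worth making because it is cheap and removes the choice of pairs after the data are seen.

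**What to change.** In the SAP:

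1. Name one decision test per primary outcome, two-sided 0.05, computed from per-subject difference scores and not conditional on the omnibus F: **orange minus dim** for gait, **room minus orange** for alertness. Difference scores also remove the sphericity assumption.
2. Report the pattern contrasts (dim, orange, room: −2, +1, +1 for gait; −1, −1, +2 for alertness) and the omnibus F as supportive.
3. For the equality parts (orange and room on gait; dim and orange on alertness), state a margin in advance and judge the confidence interval for the difference against it. A non-significant difference is not evidence of equality.
4. State plainly that each subject is seen in all three lights, since this sets the error df.
5. State how the two primary outcomes are handled together. Two independent tests at 0.05 carry a 1 − 0.95² = 9.75% chance of at least one false positive. Naming one comparison per outcome does not settle this.

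The cost is a few lines of text, with no extra data or subjects. What is given up is that any other pattern of difference, such as room light alone improving gait, would count only as supportive.
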